## STUDY PROTOCOL PLAN

### **Objectives:**

The objectives of our study have been the following:

#### General:

- Evidence changes in pressure in the plantar support in dynamics after treatment with deep dry needling in the tibialis posterior myofascial trigger point.

#### Specific:

- Analyze the variation of the plantar dynamics in the subjects without intervention to avoid learning bias of the methodology of the baropodometric registry.
- Evidence if deep dry needling is effective in the treatment of myofascial trigger point.
- Observe if there are differences in the treatment taking into account the covariates measured such as age, sex, and physical activity practice and body mass index.

Volunteers who want to participate in the study will read the general information of the study and sign the informed consent to participate in the study.

Once the informed consent has been read and delivered, the evaluator will check that they meet the inclusion criteria. After the data collection, a randomization (Epidat V4.0) of the selected subjects will be carried out to assign them to one of the intervention groups.

In the evaluation room, the evaluator, after taking the measurements of weight and height.

To locate the myfascial trigger point in the tibialis psoterior, the palpation technique will be used, grasping the belly of the muscle between the thumb and the 2nd and 3rd fingers. The evaluator will press the fibers with a forward and backward movement to find the taut bands. Once the taut band is found longitudinally, the nodule and the point of greatest sensitivity to pressure will be located.

Once the myofascial trigger point is located, it will be marked with a dermal marker. Those subjects in whom the myofascial trigger point can not be located with precision, will be excluded from the study.

After having marked the myofascial trigger point, the evaluator will make the subject the algometry in the myofascial trigger point. 3 measurements will be taken with an interval of 20 seconds between measurement and measurement, and the average of the three measurements obtained will be calculated.

Next, The baropodometry will be carried out. The subject will perform the march on the platform for one minute. At the moment that the baropodometer registers correctly the data will warn us.

Once the pre-intervention measurements have been made, the subject will go to the adjoining room to carry out the intervention.

The intervention sequence varied depending on the group to which the subject "Group intervention 1" (G1),

- "Intervention group 1" (G1): the deep dry needling technique will be performed with a duration of less than one minute in the tibialis posterior.

Initial position: The patient will be placed supine with an external rotation of the hip and slight knee flexion. The auditor is placed on the homolateral side.

Placement of hands: the auditor locates the myofascial trigger point in the tibialis posterior with the left hand on the inside, back of the tibia, and perform the technique with the right hand.

Technique: The inspector, with gloves, disinfects the area to be treated with 70° alcohol. Once the alcohol is applied, the intervenor locates and takes the myofascial trigger point and places the needle with the guide tube resting on the skin of the patient. The inspector holds the guide tube between the index and middle fingers lightly touch the needle with the index finger of the other hand to insert the needle perpendicularly into the skin, directing it towards the inspector's thumb. Once the needle is inserted subcutaneously, the guide tube is removed. The controller deepens the needle to myofascial trigger point, and makes fast inputs and outputs into it. The rapid exit is made to the subcutaneous cellular tissue, outside the muscle, but not outside the skin. Next, hemostasis is performed in the area. Once this hemostasis is completed, the patient is incorporated and dressed.

- "Control group (G2)": the simulated dry puncture technique will be performed.

Initial position: The patient will be placed prone. The interventor is placed on the homolateral side.

Technique: The patient lies on the stretcher without the trousers. The interventor, with the guide tube, simulates the technique of puncture in the right twin of the subject. The controller cleans the area with 70° alcohol. Once the alcohol is applied, he performs the simulated dry needling technique in a plane with his index and middle fingers with the guide tube. It is important that the subject has his head stuck in the hollow of the head of the stretcher throughout the technique to make a correct masking.

Next, a simulation of hemostasis is performed in the area. Once this simulation is finished, the patient is incorporated and dressed.

Once the intervention is done, the subject will return to the evaluation room to proceed to the evaluation immediately after the intervention (POSTINT), both algometric and baropodometric measurements. After these measurements, the subject will be summoned at the same time to return at 24 hours (POST24h) and at 72 hours (POST72h) to perform the corresponding algometric and goniometric measurements.

This study will be carried out in two adjoining rooms, with a sufficient amplitude to offer freedom of movement, both to the evaluator and the auditor and the subject of the study.

In one of the rooms will be the evaluator to perform the measurements and collect the pre- and post-intervention values. In the adjoining room will be the controller, in charge of carrying out the corresponding intervention.

Between both rooms there are about eight meters of distance without steps or unevenness, and they will maintain an identical and constant temperature.

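### Specific objective 1 relies on untreated subjects that the design does not have, so learning on the platform is mixed with the sham effect in G2 and with needling in the within-G1 change

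*Combined protocol and SAP*

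**What the plan says.** The first item under the Specific objectives is to "Analyze the variation of the plantar dynamics in the subjects without intervention to avoid learning bias of the methodology of the baropodometric registry". The procedure that follows describes these steps:

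- **Assignment.** After data collection, "a randomization (Epidat V4.0) of the selected subjects will be carried out to assign them to one of the intervention groups". Two groups are described and neither is untreated.
- **G1.** "the deep dry needling technique will be performed with a duration of less than one minute in the tibialis posterior".
- **G2.** "the simulated dry puncture technique will be performed". The operator uses a guide tube and "simulates the technique of puncture in the right twin of the subject", with alcohol cleaning and simulated hemostasis.
- **Platform recording before the procedure.** "The subject will perform the march on the platform for one minute". No practice walk and no repeat baseline is described.
- **Sequence.** "Once the pre-intervention measurements have been made, the subject will go to the adjoining room to carry out the intervention". Algometry and baropodometry are then repeated immediately afterwards (POSTINT).
- **Later visits.** At 24 h and 72 h the protocol lists algometric and goniometric measurements. Baropodometry is not named.

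The Statistical Analysis Plan tests equality of means in both groups and over four times by a repeated-measures ANCOVA. It names no analysis for objective 1 and does not name the group-by-time term as the test of needling.

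**The concern.** The objective presupposes a set of recordings in which nothing but repetition happens between one walk and the next. The design offers none before the procedure, because there is a single PRE walk and every subject then goes to the intervention room. If the phrase is meant to denote G2, the change in G2 still combines familiarity with the platform and whatever handling the leg and expecting treatment may do.

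Two conclusions are at stake. First, a result reported under objective 1 could be read as showing how much learning there is, or that there is none, when the data cannot show either. Second, the general objective asks for pressure changes after needling and names no comparator. Someone could therefore report the change within G1 as the needling effect, and learning is a direct rival explanation for that change. The only baseline for either reading is the subject's first recording in the study, the one most exposed to unfamiliarity.

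**Working it through.** The documents give no sample size, standard deviation, effect size or reliability, so there is no figure to reproduce. The check is which quantities the recordings can estimate.

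**Notation, for the mean change from PRE to POSTINT.** L is learning or repeat-test change, S is the sham or non-specific effect, and N is the specific effect of needling. Effects are assumed additive, with L and S equal in the two arms.

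**1. Design as written.**
- G1 change = L + S + N
- G2 change = L + S

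The coefficient rows are (1, 1, 1) and (1, 1, 0), which have rank 2 for three unknowns. For any constant k, the values (L + k, S − k, N) give the same two means. Hence:
- L alone is not estimable, and S alone is not estimable.
- L + S is estimable, from the G2 change.
- N is estimable: (L + S + N) − (L + S) = N.

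A G2 change near zero would not show absence of learning, since L = +d with S = −d also gives zero.

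**2. What the contrast rests on.** If L and S differ by arm, G1 minus G2 equals N + (L₁ − L₂) + (S₁ − S₂). Randomisation and the same PRE and POSTINT sequence support L₁ = L₂. That S₁ = S₂ is an assumption: the sham is done prone at a different site, the needling supine.

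**3. With a second walk before the procedure.** Let L₀ be learning from PRE1 to PRE2, and let L now run from PRE2 to POSTINT.
- PRE2 − PRE1, all subjects = L₀
- G1, PRE2 to POSTINT = L + S + N
- G2, PRE2 to POSTINT = L + S

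The rank is 3 for four unknowns. L₀ and N are estimable. L is still not estimable by itself. If learning is assumed to have plateaued by PRE2 (L = 0), the G2 change estimates S.

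**4. With an untreated, repeatedly measured arm.** Its change is L, the rank is 3 of 3, and L, S and N are all estimable.

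**5. Precision, a side issue.** Averaging two baselines can reduce the ANCOVA residual variance if baseline is a covariate and there is no learning shift. With r the correlation of one PRE walk with the later recording and q the correlation of PRE1 with PRE2, the residual fraction goes from 1 − r² to 1 − 2r²/(1 + q). Both r and q are assumptions.

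| r | one walk | mean of two, q = r | reduction | mean of two, q = 0.9 | reduction |
|---|---|---|---|---|---|
| 0.5 | 0.750 | 0.667 | 11% | 0.737 | 2% |
| 0.7 | 0.510 | 0.424 | 17% | 0.484 | 5% |
| 0.8 | 0.360 | 0.289 | 20% | 0.326 | 9% |

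The gain runs from about 2% to 20% depending on values the documents do not give. It belongs to the mean of the two walks and not to PRE2 alone, so it is not a reason for the change proposed here.

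**The case against.** The strongest reply is that the objective speaks of avoiding learning bias, and that this does not require isolating learning. Subtracting the G2 change is enough, and in a roughly translated text the untreated subjects are most naturally the control arm. Subjects are randomised, both arms follow the same PRE and POSTINT sequence, and the SAP includes both groups. A baseline affected by unfamiliarity is affected in both arms.

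This stands as far as the between-group comparison goes. A reader might infer from the missing untreated group that learning cannot be separated from the needling effect at all. The documents do not support that, since common learning cancels in the difference in change. A reader might also infer that no interval between recordings is free of a procedure. That goes too far as well: if platform recordings are made at 24 h and 72 h, no new procedure is described between POSTINT and those visits, although carry-over could still affect them.

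The reply does not rescue the objective as worded. Analysing variation in G2 by itself neither measures learning nor corrects for it, and the SAP does not name the subtraction that would correct for it.

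It is also fair to say that the second walk captures only the first step of learning, and that the randomised comparison does not need it. Both are true. Its value is a procedure-free estimate of early learning, which the stated objective calls for, and a baseline less exposed to unfamiliarity.

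**Conclusion.** The point holds in a limited form. Objective 1 cannot isolate learning: in G2 learning is mixed with the sham or non-specific effect, and in the within-G1 change it is mixed with both that effect and needling. The randomised difference in change between G1 and G2 remains a valid way to remove learning shared by the arms. Reading it as the specific needling effect rests on additivity and on equal learning and equal non-specific effects in both arms; the last of these is uncertain because position and site differ.

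The size of the learning effect cannot be stated, because the documents give no data on it and the design as written would not yield any. This is not a fatal flaw. It limits what may be concluded, and the correction is cheap enough that it should be made.

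**What to change.** 1. Record two one-minute walks, PRE1 and PRE2, in every subject before the intervention room. Report PRE2 minus PRE1 with its 95% confidence interval as the estimate of early learning, and state that learning after PRE2 is assumed to plateau.
2. Fix PRE2 as the baseline in advance. Do not choose between PRE2 and the mean of both after looking for a shift: that selects the baseline from the data, and failing to see a shift does not show there is none.
3. In the SAP, name the between-group difference in change (group-by-time) as the test of needling, and state that no conclusion about needling will be drawn from the change within G1.
4. If the second walk is not added, reword objective 1 as change over the platform recordings in the sham group, and say that this does not separate learning from sham effects.
5. Before stating how many platform recordings there are, reconcile the procedure section, which lists goniometric measurements at 24 h and 72 h, with the four times in the SAP.

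The cost is one to two extra minutes per subject on a platform already in use, with no extra visit. Items 3 to 5 need edits to the text only.

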### **Statistical Analysis Plan (SAP)**

For the qualitative variables we will make some frequency tables. On the other hand, for the quantitative variables, maximums, minimums, mean values and the standard deviation will be calculated.

To check the homogeneity of the intervention and control groups, the association with the explanatory variables sex, age, body mass index and sport hours will be measured using the Chi-square test or the T-student test as appropriate.

The equality of mean values of each dependent variable will be tested, both in the intervention group and in the control group, as in the four measurement times by means of an ANCOVA procedure (analysis of the covariance with repeated measures).

The confidence interval will be 95%

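### Does the third specific objective, on age, sex, activity and BMI, lack an analysis in the SAP?

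*Combined protocol and SAP*

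**What the plan says.** The objectives section gives one general objective (plantar pressure in walking after needling) and three specific ones. The third is "Observe if there are differences in the treatment taking into account the covariates measured such as age, sex"; its list also takes in activity level and BMI.

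The SAP is a few sentences long. The four variables appear in it once, in a step whose stated purpose is "To check the homogeneity of the intervention and control groups". There, "the association with the explanatory variables sex, age, body mass index and sport hours will be measured using the Chi-square test" or a t test. The next sentence is the only outcome analysis. It tests equality of means of each dependent variable across the two groups, "as in the four measurement times by means of an ANCOVA procedure (analysis of the covariance with repeated measures"). It lists no covariate, interaction or subgroup.

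The four times are one before treatment ("Once the pre-intervention measurements have been made", the participant goes for the intervention), one immediately after it, and two more when participants "return at 24 hours (POST24h) and at 72 hours (POST72h").

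**The concern.** The objective can be read in two ways:

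- **Adjustment:** the treatment effect, taking account of age, sex, activity and BMI.
- **Effect modification:** whether the treatment effect differs by age, sex, activity or BMI.

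The SAP does not say which is meant. The homogeneity tests compare the distribution of each variable between the arms and never use an outcome, so they answer neither version. The ANCOVA sentence does not say that the four variables enter the model.

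If the gap mattered, the meaning of the objective, the covariate list and any interaction terms could all be chosen after the data were seen. With several covariates and more than one outcome, that leaves room for selective reporting.

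**Working it through.** The main question is textual. The arithmetic only shows how much depends on it.

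**1. Objective against SAP.** The objective calls age, sex, physical activity and BMI covariates. The SAP calls sex, age, BMI and sport hours explanatory variables, and its next sentence specifies an analysis of covariance. These are the same four items, apart from the label for activity. No other covariates are named anywhere. The baseline outcome is a less natural candidate, because the SAP analyses four measurement times and the pre-intervention value is one of them, so it is already a response. The likeliest reading is adjustment for these four variables.

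**2. What the unstated list does to the treatment contrast.** Take baseline as one of the repeated responses and complete data. The treatment effect at time t is the between-group difference in mean change:

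effect(t) = [mean(Y_t) − mean(Y_0)] in G1 − [mean(Y_t) − mean(Y_0)] in G2.

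A covariate that is constant over time and enters additively contributes the same amount to Y_t and Y_0, so it cancels from each change. In one simulated data set (80 participants, four times, random intercept, all assumed) the three contrasts were 0.961, 0.899 and 0.914 with and without the covariates, with standard error 0.342 both ways. They moved only when covariate-by-time terms were added, to 1.024, 0.954 and 0.918. Because allocation is randomised, the adjusted and unadjusted contrasts target the same effect and differ by chance imbalance.

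**3. What effect modification could deliver.** Let V be the variance of the overall effect and q the share of participants in one level of a binary covariate, with arms balanced within levels. The two level-specific effects have variances V/q and V/(1−q). Their difference has variance V/[q(1−q)], so

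SE ratio = 1/√[q(1−q)].

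| Assumed split | q(1−q) | SE ratio |
|---|---|---|
| 50:50 | 0.25 | 2.00 |
| 60:40 | 0.24 | 2.04 |
| 70:30 | 0.21 | 2.18 |
| 80:20 | 0.16 | 2.50 |

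Even in the best case, matching the precision of the overall effect would take 2.00² = 4 times as many participants. The document gives neither a sex split nor a sample size.

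**4. Multiplicity.** One joint interaction test per covariate gives four tests per outcome. Assuming independence, the chance of at least one false positive at 5% is 1 − 0.95⁴ = 18.5%. For two outcomes (an assumed number) it is 1 − 0.95⁸ = 33.7%.

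**5. A possible modelling trap.** If modification of size d were constant over three post-treatment times, a plain group-by-covariate term averaged over all four times would estimate (0 + d + d + d)/4 = 0.75d. The SAP proposes no such term, so this describes a mistake someone might make and is no consequence of the plan. The number of times is also unsettled for plantar pressure. The procedure text assigns algometry and goniometry to the 24 h and 72 h visits, while the SAP speaks of four times. With two times the same average would be (0 + d)/2 = 0.5d.

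**The case for a change.** The strongest case for a change is that the wording about differences in the treatment naturally suggests effect modification. Entering four covariates additively would not address that, whatever ANCOVA is taken to mean. On that reading one of three specific objectives has no stated analysis. A sentence in the SAP would settle the matter at no cost in data, and naming the terms beforehand guards against picking subgroups afterwards.

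Part of this stands. The objective is ambiguous, the homogeneity tests are no evidence on it, and the SAP would be better for naming its covariates. It does not follow that the plan goes wrong. The effect-modification reading is possible but not established, and a remedy that depends on it would first have to decide what the authors meant. No rule the plan does state has been shown to give a wrong result. Simply instructing analysts to enter the four variables would also do less than it appears to: by step 2, with baseline kept as a response and complete data, it would leave the treatment contrasts where they were.

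**Conclusion.** No change to the plan follows. This is a gap in detail of a familiar kind: an ANCOVA whose covariates are not listed, in a document that names only four candidates. An analyst would sensibly adjust for those four whatever the homogeneity tests show, and would treat any comparison of effects between subgroups as exploratory.

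The reach is one secondary question, the last of three specific objectives and worded as something to observe. The comparison of needling with simulated needling does not depend on it. If effect modification was meant, the plan does lack an analysis for it, but the estimates would carry at least about twice the standard error of the overall effect and an 18.5% chance of a false lead per outcome. They could support no firm claim however they were specified.

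This conclusion assumes that adjustment is the intended meaning, or that any subgroup finding is presented as exploratory. It would weaken if a report made a confirmatory claim that the treatment works better in one sex, age, activity or BMI group. The figures rest on the assumed splits, balance of arms within levels and independence of tests stated above.

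### No harms are asked about at any of the three post-intervention assessments or summarised in the SAP, so needling harms cannot be reported by arm

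*Combined protocol and SAP*

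**What the plan says.** The procedures stand in the Study Protocol Plan, in the text that follows the specific objectives.

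- **G1.** The needle technique is described thus: "The controller deepens the needle to myofascial trigger point, and makes fast inputs and outputs into it". Then: "Next, hemostasis is performed in the area".
- **G2.** The operator works with the guide tube on a different muscle: "he performs the simulated dry needling technique in a plane with his index and middle fingers with the guide tube". Hemostasis is only simulated, and no needle insertion is described.
- **POSTINT.** The subject goes back "to proceed to the evaluation immediately after the intervention (POSTINT), both algometric and baropodometric measurements".
- **Later visits.** The subject is asked "to return at 24 hours (POST24h) and at 72 hours (POST72h"), and the purpose of both visits is "to perform the corresponding algometric and goniometric measurements".
- **Evaluator.** The paragraph on the two rooms gives this role: "the evaluator to perform the measurements and collect the pre- and post-intervention values".

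The general objective is "Evidence changes in pressure in the plantar support in dynamics after treatment with deep dry needling". The Statistical Analysis Plan (SAP) covers descriptive statistics, tests of baseline homogeneity on sex, age, body mass index and sport hours, and a repeated-measures ANCOVA of each dependent variable by group and over four time points. It names no harms variable.

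**The concern.** One arm undergoes an invasive procedure and the other does not. The plan itself expects some bleeding in G1, because it provides for hemostasis. Subjects are then seen three times within 72 hours, when soreness, haematoma or altered sensation could be asked about at almost no cost, but no such question is scheduled. The trial also asks whether needling is effective, and an answer on efficacy without harms by arm is incomplete. Soreness and transient events cannot be reliably reconstructed afterwards.

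There is a lesser consequence for interpretation. A sore leg may load the foot differently, and the general objective states no direction of benefit. A change in dynamic plantar pressure could therefore be read as the result of treating the trigger point when part of it is a response to soreness. The planned data contain nothing against which to check that reading.

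**Working it through.** The plan states no sample size, event rate or harm rate, so there is no figure of its own to reproduce. The check is a reading of the whole available text, set out by assessment.

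| Assessment | Measurements listed | Harms question |
|---|---|---|
| Before intervention | algometry, baropodometry | none |
| POSTINT | algometry, baropodometry | none |
| POST24h | algometry, goniometry | none |
| POST72h | algometry, goniometry | none |

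1. **Count.** Harms are solicited at 0 of 3 post-intervention assessments. This comes from the documents and needs no assumption.

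2. **Exposure.** By protocol, every G1 subject is punctured and no puncture is described for G2. Harms of puncture can therefore arise essentially in G1 only, and the sham gives no substitute record of them.

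3. **Analysis.** The SAP's general provision of frequency tables for qualitative variables could hold harms items, but none is collected. The named covariates are age, sex, physical activity and body mass index. None of them captures soreness.

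4. **Would a form pick anything up?** Assumed values, none from the documents: a harm with 10% incidence in G1, and 20 to 50 subjects in that arm. The chance of at least one case is 1 − 0.9^20 = 0.878 at the lower size and 1 − 0.9^50 = 0.995 at the upper. This is an illustration only, and the conclusion does not depend on it.

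5. **Gait.** Let s1 and s2 be the shares of G1 and G2 that are sore, and d the mean shift in plantar loading among sore subjects. Soreness then moves the group contrast by (s1 − s2) × d. The documents give none of the three. G2 soreness need not be zero, because both arms have the trigger point palpated and pressed with the algometer. Nor need d have the same direction in every subject. No size is therefore put on this part.

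6. **Visits affected by the gait caution.** The visit schedule lists baropodometry at POSTINT but goniometry at 24 h and 72 h. The SAP tests each dependent variable at four times, which would require plantar pressure at those visits too. The two places conflict and must be reconciled. As the schedule stands, the caution is supported at POSTINT only.

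**The case against.** The strongest reply concerns the treatment contrast. Soreness caused by needling is an effect of needling, so a randomised difference in plantar pressure remains a valid total effect, and the general objective asks only whether pressure changes after treatment. That stands. A reader might infer that the G1–G2 comparison is biased, or that the gait results at every visit are compromised. The documents support neither: only the interpretation is at stake, and only POSTINT clearly carries a gait recording after the intervention.

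A second reply is that algometry at the needled point already registers local tenderness. It does so in part. But it is itself an outcome, it does not measure soreness on walking, it cannot separate needling tenderness from trigger-point sensitivity, and it records no injury.

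Third, a reader might infer that events would be discarded. The text shows only that nothing is scheduled to elicit them; it does not say that a spontaneous report would be ignored. The consent pages are not in the reviewed text and may name risks, but naming risks is not a plan to record events by arm.

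Finally, a soreness record will not split the two pathways. Soreness arises after randomisation and is likely to track arm closely. A rule withholding attribution wherever soreness differs between arms would have no natural threshold and might apply almost automatically. The record supports honest reporting, not a mediation claim.

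**Conclusion.** The point holds as a gap in harms ascertainment and reporting. There are 0 of 3 post-intervention assessments with a harms question and no harms summary in the SAP, in a trial where one arm is needled and the other has no puncture described. This rests on the text as written and on no assumed figure. It is more than missing detail, because data that are not collected cannot be added at analysis. It should be corrected before enrolment, although the trial can run without it.

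The gait element is a secondary caution on interpretation, without a size. It applies at POSTINT, and at 24 h and 72 h only if baropodometry is in fact done then.

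**What to change.** **Protocol, post-intervention evaluation.** Add a one-page form in both arms at baseline and at the three existing assessments.

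- The subject completes it and the evaluator does not see it. The operator should not collect it, because that person knows the allocation and harms would then be ascertained unblinded.
- It is filled in after the instrument readings, so that the questions do not prime gait.
- At all four assessments it asks for soreness at rest and on walking (0–10), as it was before that visit's measurements, so that tenderness from the algometer is not counted.
- At the three post-intervention assessments it also asks about bleeding or haematoma, numbness or tingling, and faintness since the intervention.
- At 72 h it records whether any item is still present.

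**SAP.** Add a descriptive table of these items by arm and visit. Report the POSTINT plantar-pressure result alongside walking soreness by arm, and describe that result as the total effect of needling.

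**Reconcile** the measurements listed for 24 h and 72 h with the SAP's four time points, so that it is clear at which visits plantar pressure is recorded.

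**Cost.** About one minute per assessment and one extra table, with no new visits or staff. The questions may draw attention to soreness, or cue subjects about their allocation. Placing the form after the readings limits the first effect at that visit but does not remove the second.

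### The 24 h and 72 h visits call for goniometry, which the plan describes nowhere else, and no available text schedules baropodometry at those visits

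*Combined protocol and SAP*

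**What the plan says.** The general objective concerns dynamic plantar pressure: "Evidence changes in pressure in the plantar support in dynamics after treatment with deep dry needling". The study procedures, which follow the specific objectives, describe two outcome instruments before the intervention. For algometry, "3 measurements will be taken with an interval of 20 seconds between measurement and measurement", and the three are averaged. For plantar pressure, "Next, The baropodometry will be carried out. The subject will perform the march on the platform for one minute".

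Immediately after the intervention (POSTINT) the same pair is repeated: "both algometric and baropodometric measurements". The next sentence brings subjects back at 24 hours (POST24h) and 72 hours (POST72h) "to perform the corresponding algometric and goniometric measurements".

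The SAP names no outcome. It states "The equality of mean values of each dependent variable will be tested", between the groups as well "as in the four measurement times by means of an ANCOVA procedure" with repeated measures.

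**The concern.** Two adjacent sentences of the schedule name different instruments, and the second names one that has not been introduced. The sentence is operative text: it is the only available statement of what is measured at two of the four times. The instrument that drops out of it is the one that serves the general objective.

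Goniometry is a real and different measurement, so the word cannot be dismissed as meaningless. If it were followed, there would be no plantar-pressure data at 24 or 72 hours and nothing could be concluded about plantar pressure at those times. The goniometric values collected instead would have no pre-intervention value to be compared with. A recording missed at either visit cannot be made later.

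**Working it through.** No sample-size, power or alpha calculation bears on this point. The check is a count of scheduled assessments, set against the SAP's four times.

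**Mentions in the available text** (front matter was removed before review, so this covers the objectives, procedures and SAP)

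- Words for algometry: 3 (one in the pre-intervention procedure, one at POSTINT, one at the late visits).
- Words for baropodometry: 4 (one in the first specific objective, two in the pre-intervention procedure, one at POSTINT).
- Words for goniometry: 1 (the late visits only).

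**Assessments per instrument, as written**

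| Instrument | Pre-intervention | POSTINT | POST24h | POST72h | Total |
|---|---|---|---|---|---|
| Algometry | yes | yes | yes | yes | 4 of 4 |
| Baropodometry | yes | yes | no | no | 2 of 4 |
| Goniometry | no | no | yes | yes | 2 of 4 |

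**Assessments per instrument, reading the word as *baropodometric***

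| Instrument | Pre-intervention | POSTINT | POST24h | POST72h | Total |
|---|---|---|---|---|---|
| Algometry | yes | yes | yes | yes | 4 of 4 |
| Baropodometry | yes | yes | yes | yes | 4 of 4 |
| Goniometry | no | no | no | no | 0 of 4 |

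**Comparison with the SAP.** The visits count to four, and so do the algometry assessments on either reading. Baropodometry reaches four only if the word is replaced. A time factor with *k* levels has *k* − 1 degrees of freedom. The SAP's four times give 4 − 1 = 3. Baropodometry as written gives 2 − 1 = 1, which is the contrast between pre-intervention and POSTINT. The immediate change in plantar pressure can therefore still be estimated and compared between groups, but the planned four-time comparison cannot be made.

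**Which reading is more likely.** Three points favour a slip:

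- The late-visit sentence refers to *corresponding* measurements, which points back to measurements already described, and goniometry has not been described.
- The preceding sentence gives the parallel pair of instruments.
- The SAP compares every dependent variable over four times.

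None of these schedules baropodometry at 24 or 72 hours. That plantar pressure is among the SAP's four-time outcomes is itself an inference from the general objective, which states no time point. Algometry alone would satisfy the SAP's wording.

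**The case against.** The strongest reply is that this is a plain one-word slip that the documents largely resolve. Only two outcome instruments are described before the intervention, so leaving plantar pressure out of the SAP's dependent variables would be a strained reading. The first specific objective, on learning bias in the baropodometric recording, presupposes that baropodometry is repeated. Terminology is loose throughout: what appears to be a single operator goes by several different titles. An evaluator given no joint, device or procedure could hardly carry out goniometry without asking. On this view the point is a low-priority text correction.

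Much of this stands. The slip reading is the more likely one, and on it there is no data loss if baropodometry is recorded. The learning-bias objective adds some support to it. But these arguments imply late baropodometry without scheduling it, and the one sentence that does schedule the late visits says something else. A reader comparing reported results with the plan could not tell whether plantar-pressure data at 24 and 72 hours were pre-specified.

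It is also fair to say that the documents do not give the trial's status. If the visits are over, correcting the text cannot change what was collected, but clarification is still needed to establish which data exist at the late visits.

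**Conclusion.** The concern holds and should be fixed. The mismatch in wording is certain; any loss of data is not. On the more likely reading, baropodometry is at 4 of 4 times, goniometry at none, and the error is confined to the text. On the literal reading, baropodometry is at 2 of 4 times and goniometry at 2 of 4 without a pre-intervention value, so the four-time analysis cannot be run for the outcome of the general objective. Algometry is unaffected on both readings.

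This rests on two assumptions: that the removed front matter does not define goniometry or schedule late baropodometry, and that plantar pressure is one of the dependent variables the SAP means to test over four times. Even if the front matter did define goniometry, the two adjacent schedule sentences would still name different instruments.

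**What to change.** Ask the investigators to confirm what is measured at POST24h and POST72h, before the first follow-up visit if visits have not begun.

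- **If it is a slip:** replace *goniometric* with *baropodometric* in the late-visit sentence, so that both instruments are recorded at all four times. This costs one word. Subjects already attend both visits, and the recordings amount to 2 visits × 1 minute = 2 minutes of walking per subject, set-up not counted. On this reading those recordings were intended anyway.
- **If late baropodometry is not intended:** state in the SAP that the four-time analysis applies to algometry only and that baropodometry is compared between pre-intervention and POSTINT. Then reconcile or remove goniometry. This costs one sentence and one decision.
- **If goniometry is really intended:** give it a procedure, a pre-intervention measurement and a place in the objectives and analysis, and state separately whether baropodometry is also recorded at the late visits.

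If follow-up is already complete, the same clarification should record which instrument was used at 24 and 72 hours.
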